11.2. Statistical and Analytical Plans

- a. **Primary outcome analysis:** The primary analysis will be performed on the changes of glycemic profiles, glycemic indexes and targeted metabolites from early to mid-pregnancy (baseline visit and visit 1 in this study) in relation to GDM phenotypes. Time-series analysis and linear regression will be applied for this analytical plan.
- b. **Secondary outcome analysis:** The secondary analysis will be performed on the association between OGTT 0, 1-hr and 2-hr glycemic values (continuous variables) and GDM phenotypes (categorical variables) (as exposure) (visit 1 in this study) with treatment strategies (diet alone, diet and metformin, diet and metformin and/or insulin) received in late pregnancy (as outcomes) (visit 2 in this study). Ordinal logistic regression will be applied for this analytical plan.
- c. **Exploratory outcomes analysis:** In order to build machine learning prediction models, both stepwise logistic regression and ensemble random forest methods will be applied for variable selection. ([name] needs to nourish this).

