1.2. Rationale and justification for the Study

Therefore, it is necessary and clinically significant to address the heterogeneity in GDM in terms of cardio-metabolic alteration and treatment responses, especially among a higher risk group of overweight and obese pregnant women from different ethnic background in Singapore. In this proposed pregnancy cohort, we aim to conduct a longitudinal study among 800 overweight ($23-24.9$ kg/m 2) or obese (≥ 25 kg/m 2) singleton pregnant women—without a history of diabetes and composed of all ethnicities (mainly Chinese, Malay and Indian)—in a Singaporean tertiary hospital (National University Hospital, NUH) during their first trimester. We intend to recruit all pregnant women no later than 14 weeks of gestation (including 13W6D) and screen them for GDM during 15-30 weeks of gestation. We will further follow up the GDM women (~200) from 34-36 weeks gestational to delivery. We will characterize heterogeneous GDM phenotypes using a comprehensive cardio-metabolic examination throughout pregnancy.

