2. HYPOTHESIS AND OBJECTIVES

Our primary outcome will be unique glycemic profiling recorded via a continuous glucose monitoring device and distinctive cardio-metabolic biomarkers alteration from early to late pregnancy that determine different GDM phenotypes. Our secondary outcome will be specific treatment response according to different GDM phenotypes in late pregnancy. We hypothesize that GDM heterogeneity might not only be differentiated by patterns of glycemic profiles and signatures of cardio-metabolic biomarkers or metabolites throughout pregnancy, but also lead to phenotype-specific treatment response in late pregnancy. Furthermore, given the early discovery of unique glycemic profiles and cardio-metabolic biomarkers and metabolites among GDM subjects in the first trimester, we also plan to explore a prediction model using machine deep learning technique.

Specific Aim 1 (Primary Outcome): To characterize GDM phenotypes through trajectories of glycemic profiling and cardio-metabolic biomarkers or metabolites from early to late pregnancy.

Hypothesis: Different GDM phenotypes manifest specific patterns of glucose profiling (i.e. mean glucose level, TIR [% time in range between 3.5-7.8 mmol/L, glycemic variability indices]), altered levels of insulin sensitivity and secretion measures (i.e. homeostatic model assessment of insulin resistant [HOMA-IR], HOMA- β , Insulinogenic index/HOMA-IR, Matsuda index), fasting, 1-hour and 2-hour insulin, fasting c-peptide, HbA1c, fasting adipokines [e.g. leptin and adiponectin], and different combination of targeted lipidomic and metabolomic metabolites (i.e. Acylcarnitines, fatty acids and amino acids).

Specific Aim 2 (Secondary Outcome): To study treatment response linked to different GDM phenotypes.

Hypothesis: GDM phenotypes such as fasting glucose impairment alone and both fasting and post-challenge glucose abnormality will require immediate attention of medication (metformin and/or insulin), while GDM phenotypes such as different pattern of post-challenge glucose intolerance alone will require more diet and life style modification other than medication.

Exploratory Aim 1 (Machine Learning prediction model): To use machine learning to develop a prediction model for GDM diagnosis in the first trimester.

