5. STUDY DESIGN

5.1. Summary of Study Design

As shown in the figure above, we will recruit participants attending NUH antenatal clinic during their first trimester. We will receive consents and collect blood samples at screening phase and/or baseline visit. Blood samples, CGM and fecal collection will align with the antenatal genetic visit. Then we will review them during 15-30 weeks and 34-36 week gestation. All three visits involve blood drawn and continuous glucose monitoring application.

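### The primary outcome and Aim 1 run to late pregnancy, but the protocol's primary analysis ends at visit 1

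*Protocol*

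**What the plan says.** Protocol section 2 sets the primary outcome as CGM-based glycemic profiling together with "distinctive cardio-metabolic biomarkers alteration from early to late pregnancy that determine different GDM phenotypes". Specific Aim 1, labelled there as the primary outcome, is "To characterize GDM phenotypes through trajectories of glycemic profiling and cardio-metabolic biomarkers or metabolites from early to late pregnancy". Section 1.2 points the same way: "We will characterize heterogeneous GDM phenotypes using a comprehensive cardio-metabolic examination throughout pregnancy".

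The data collection matches that span. Section 1.2 states: "We will further follow up the GDM women (~200) from 34-36 weeks gestational to delivery". Section 5.1 adds: "All three visits involve blood drawn and continuous glucose monitoring application". Section 6.3 places baseline at 5-13 weeks and visit 1 at 15-30 weeks, both for all participants, and visit 2 at 34-36 weeks for women with GDM only.

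Section 11.2 then lists three analyses. The primary one concerns changes "from early to mid-pregnancy (baseline visit and visit 1 in this study) in relation to GDM phenotypes". The secondary one relates visit-1 OGTT values and phenotype to the treatment strategy "received in late pregnancy (as outcomes) (visit 2 in this study"). The exploratory one selects variables for prediction models. Section 2 gives that aim as: "To use machine learning to develop a prediction model for GDM diagnosis in the first trimester".

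**The concern.** The objective and the analysis meant to answer it cover different periods. A statistician who follows section 11.2(a) leaves the late part of Aim 1 unanswered. One who follows section 2 departs from the stated primary analysis. While both texts stand, the window behind the headline result is not fixed in advance and could be settled after the data are seen.

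There is also a question of purpose. About 200 women with GDM are asked for a further blood draw and a further period of CGM wear at 34-36 weeks, and the protocol's analysis section gives those measurements no role.

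**Working it through.** The protocol gives no figure to reproduce on this point. The check sets the texts side by side.

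**1. Window of the primary outcome**

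| Place in protocol | Window |
|---|---|
| Section 2, primary outcome | early to late pregnancy |
| Section 2, Specific Aim 1 | early to late pregnancy |
| Section 11.2(a), primary analysis | early to mid-pregnancy, baseline and visit 1 |

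**2. Can visit 1 count as late pregnancy?** Its window reaches 30 weeks (section 6.3), so one could try this reading. Section 11.2 rules it out: part (a) calls baseline to visit 1 early to mid-pregnancy, and part (b) ties late pregnancy to visit 2.

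**3. Does restricting visit 2 to women with GDM explain the gap?** No. Aim 1 characterizes GDM phenotypes, and those are exactly the women seen at visit 2.

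**4. Which stated analyses use visit-2 CGM or blood?**

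| Analysis in section 11.2 | Data used | Visit-2 CGM or blood? |
|---|---|---|
| (a) primary | baseline and visit 1 | no |
| (b) secondary | visit-1 OGTT values and phenotype; treatment received by visit 2 | no |
| (c) exploratory | prediction in the first trimester (section 2) | no |

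Count: 0 of 3.

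**5. Which measures could be carried to visit 2 with the data planned?** Section 6.3 gives a random blood sample at baseline, a fasting sample at visit 1 and a random sample at visit 2. It records an OGTT only at visit 1.
- CGM measures (mean glucose, time in range, variability) are planned at all three visits and do not depend on a fasting sample.
- Markers defined on fasting or OGTT samples (the HOMA, insulinogenic and Matsuda indices; fasting, 1-hour and 2-hour insulin; fasting c-peptide; fasting adipokines) cannot be formed as defined from a random visit-2 sample.
- The random baseline sample raises the same difficulty for their change from baseline to visit 1. That is a separate conflict, and aligning the window does not resolve it.

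**6. Multiplicity if the longer window stays primary.** Section 11.1 allows for 10 outcomes with a Bonferroni correction: 0.05 / 10 = 0.005 per outcome. A visit-2 comparison promoted to primary has to sit inside that family.

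**The case against.** The strongest reply is that the limit in section 11.2(a) may be deliberate. Values at 34-36 weeks come after treatment has begun in some women, so early to mid-pregnancy gives a cleaner comparison of phenotypes. Visit 2 already has a stated role as the time point for the secondary outcome. On this view section 2 is merely worded too widely. This is plausible, but the protocol does not say it, and section 2 would still need correcting. It bears on which text to change, not on whether one must change.

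A second reply is that only the protocol is at hand, and supportive analyses are commonly left to an analysis plan. That stands as far as it goes. A reader might infer that the visit-2 measurements will never be analysed; the documents do not support that, since section 11.2 excludes no further analysis and a separate plan could contain one. What cannot be left to such a plan is the contradiction, because the protocol does not defer the primary window. It states two.

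A reader might also infer that the primary analysis should simply be extended to visit 2 for every marker in Aim 1. The sampling scheme in section 6.3 does not support that for fasting- or OGTT-based markers.

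**Conclusion.** The concern holds as a contradiction within the protocol: sections 2 and 11.2(a) give different windows for the same primary outcome, and the visit labels in section 11.2 leave no reading that reconciles them. As written, the primary analysis supports conclusions about early to mid-pregnancy only, and 0 of the 3 stated analyses use the visit-2 CGM and blood data from about 200 women with GDM.

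The conclusion rests on the protocol alone and on its own labelling of visit 2 as late pregnancy. It is not a claim about bias, power or error rate. A reader might take the mismatch to invalidate the sample size, but nothing in the comparison of windows bears on that. The point should be corrected before analysis. It is modest in scale, because this is an observational cohort and a change of text using data already planned is enough.

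**What to change.** Make sections 2 and 11.2(a) state one window, in either of two ways.

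1. Reword the primary outcome and Aim 1 to early to mid-pregnancy, leaving the window in section 11.2(a) as it is. Add to section 11.2 a secondary analysis, among women with GDM, comparing CGM measures across baseline, visit 1 and visit 2 by phenotype. A repeated-measures model with visit, phenotype and their interaction is one example.
2. Keep early to late pregnancy for the CGM measures only, and extend section 11.2(a) to visit 2 for them. Name the term to be tested and keep it within the 10-outcome Bonferroni family of section 11.1.

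Under either option:
- State that differences at visit 2 include the effect of treatment received, and that visit 2 has no non-GDM comparator.
- Do not claim trajectories to visit 2 for fasting- or OGTT-based markers.
- Resolve separately how change from a random baseline sample to a fasting visit-1 sample is to be handled.

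The cost is protocol text, with no new visits or samples. Option 1 narrows the primary aim. Option 2 accepts late differences that mix phenotype with treatment, and it requires the tested term and its place in the multiplicity scheme to be settled in advance.

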6.3. Study Visits and Procedures

At screening and baseline visit for all participants (5-13 weeks gestation): questionnaires will be performed by trained research coordinators. And then random blood sample will be collected during the research visit. Anthropometric and blood pressure measurement will be performed by the clinic nurse. The fecal collection kit will be handed over to the participants and it would be arranged for

courier service within one month. The continuous glucose monitoring device will be worn under the supervision of research coordinators, and the courier service will be arranged for collection same time while collecting the fecal kit. Medical record regarding fetal scan and routine blood test results will be collected.

At research visit 1 for all participants (15-30 weeks gestation): Fasting blood sample will be collected during the research visit. Anthropometric and blood pressure measurement will be performed by clinic nurse. The fecal collection kit will be handed over to the participants and it would be arranged for courier service within one month. The continuous glucose monitoring device will be worn under the supervision of research coordinators, and a courier service will be arranged together with the fecal kit collection within one month. Medical record regarding fetal growth, routine blood test and oral glucose tolerance test (OGTT) will be obtained at visit 1.

At research visit 2 only for patients diagnosed with gestational diabetes (34-36 weeks gestation): Random blood sample will be collected during the research visit. Anthropometric and blood pressure measurement will be performed by clinic nurse. The fecal collection kit will be handed over to the participants and it would be arranged for courier service within one month. The continuous glucose monitoring device will be worn under the supervision of research coordinators, and the courier service will be arranged together with the fecal kit collection within one month. Medical record regarding fetal growth and routine blood test will be obtained at visit 2.

At delivery: Pregnancy complications, gestational age at delivery, delivery mode, neonatal anthropometric biometry and medical condition during the 24 hours after delivery, treatment for GDM, Apgar score, and other pregnancy maternal and fetal outcomes information will be collected.

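### Aim 2 speaks of an immediate need for medication, but its only planned outcome is treatment category at 34-36 weeks, which cannot show how soon medication is needed

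*Protocol*

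**What the plan says.** Section 2 of the protocol states the Aim 2 hypothesis in two halves. The fasting-alone and combined phenotypes "will require immediate attention of medication (metformin and/or insulin", whereas the post-challenge phenotypes "will require more diet and life style modification other than medication". The same section sets the time point: "Our secondary outcome will be specific treatment response according to different GDM phenotypes in late pregnancy".

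Section 11.2 b takes the OGTT values and the phenotypes at visit 1 as exposure. The outcome is a three-level treatment strategy "received in late pregnancy (as outcomes) (visit 2 in this study). Ordinal logistic regression will be applied for this analytical plan". No other outcome is given for Aim 2.

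The timing comes from sections 1.2 and 6.3. The plan is to recruit women and "screen them for GDM during 15-30 weeks of gestation". The first follow-up contact reads "At research visit 1 for all participants (15-30 weeks gestation", and there "Medical record regarding fetal growth, routine blood test and oral glucose tolerance test (OGTT) will be obtained at visit 1". The next reads "At research visit 2 only for patients diagnosed with gestational diabetes (34-36 weeks gestation". Section 6.3 also lists GDM treatment among the items collected at delivery. It does not list the date on which any medication began.

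**The concern.** The first half of the hypothesis carries a time element; the outcome does not. A woman who starts medication in the first week after her OGTT and one who steps up after 15 weeks on diet alone receive the same score at visit 2. If the results are then reported as support for an immediate need, the data will not bear the claim.

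Two further matters follow from fixing the outcome at visit 2.

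- Women have very different lengths of time in which to step up before they are scored. If phenotypes differ in when the OGTT was done, part of that difference will appear as a phenotype effect.
- If the outcome is read strictly as status at visit 2, a woman who delivers before that visit has no value, and step-up after it is missed. Section 1 names preterm birth as a risk of GDM, so such deliveries are to be expected.

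**Working it through.** There is no stated figure to reproduce, because the protocol gives no sample size or effect size for Aim 2.

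**Inputs from the protocol**

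- OGTT window: 15-30 weeks (sections 1.2 and 6.3).
- Visit 2 window: 34-36 weeks, GDM women only (section 6.3).
- Outcome: treatment category in late pregnancy, visit 2; ordinal logistic regression (section 11.2 b).
- Treatment data: GDM treatment collected at delivery; no start date listed (section 6.3).

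**Inputs assumed, because the protocol gives none**

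- A constant rate h of starting medication, 0.02 to 0.05 per week, identical in every phenotype.
- Illustrative times from OGTT to visit 2. The value 12.5 weeks is the distance between window midpoints, 35 − 22.5. The pair 10 v 15 weeks is a chosen moderate difference.

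**Step 1: interval from OGTT to visit 2.** Shortest: 34 − 30 = 4 weeks. Longest: 36 − 15 = 21 weeks.

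**Step 2: what the outcome can distinguish.** Medication or diet at visit 2: yes. Early or late start: no. The 15-week delay used above fits before the earliest visit 2 for any woman whose OGTT is at or before 34 − 15 = 19 weeks, which lies inside the screening window.

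**Step 3: effect of unequal time, with no phenotype effect.** The probability of being on medication at visit 2, t weeks after the OGTT, is p = 1 − exp(−h·t). The odds ratio between two groups is [p2/(1 − p2)] / [p1/(1 − p1)].

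Worked case, h = 0.02, 10 v 15 weeks: p1 = 1 − exp(−0.20) = 0.181 and p2 = 1 − exp(−0.30) = 0.259. The odds ratio is (0.259/0.741) / (0.181/0.819) = 1.58.

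| Weeks since OGTT | h = 0.02: p1, p2 | Odds ratio | h = 0.05: p1, p2 | Odds ratio |
|---|---|---|---|---|
| 12.5 v 12.5 | 0.221, 0.221 | 1.00 | 0.465, 0.465 | 1.00 |
| 10 v 15 | 0.181, 0.259 | 1.58 | 0.393, 0.528 | 1.72 |
| 4 v 21 (limits) | 0.077, 0.343 | 6.27 | 0.181, 0.650 | 8.39 |

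The last row needs one phenotype tested entirely at week 30 and seen at week 34, and the other tested entirely at week 15 and seen at week 36. It bounds the calculation and does not describe a realistic cohort.

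**Step 4: can the timing be recovered later?** The items listed in section 6.3 give the level of treatment at delivery but not when it began. An analysis plan can add a covariate for OGTT week. It cannot analyse time to medication unless the start date is abstracted.

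**The case against.** The strongest reply is that section 2 itself places the secondary outcome in late pregnancy, and section 11.2 b analyses exactly that. The hypothesis is largely a contrast of treatment type, medication against diet and lifestyle, and a treatment category at visit 2 can examine it. One adjective, which could be read as priority rather than speed, should not condemn the design. This stands: a reader might infer that the design cannot test Aim 2, and the protocol does not support that.

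On confounding, all recruits are screened in the same window and the phenotype is known only from the OGTT result. Nothing in the protocol says that OGTT week differs by phenotype. An indirect link through risk factors is possible but undocumented. Covariates are also commonly left to the statistical analysis plan, which is not at hand. This stands too: bias is conditional, and the lack of a named covariate is not a fault in itself.

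On early deliveries, no rule excludes these women. Section 1.2 follows GDM women through to delivery, and treatment is recorded then. Their loss follows only from a strict reading of the visit 2 label.

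What survives is narrower. If *immediate* means soon after diagnosis, which is its plain sense, no planned outcome matches it, and the listed data would not allow one to be built afterwards. If it means something else, the wording needs changing.

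**Conclusion.** The point holds in limited form. Hypothesis and outcome disagree within Aim 2: one refers to immediacy, the other to treatment status 4 to 21 weeks after the OGTT. The medication-against-diet comparison remains testable; the speed of need does not. The fault lies in the outcome definition and the data items, not in the cohort design.

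The varying interval adds noise in any case. It becomes bias only if OGTT week differs by phenotype. Under an assumed constant start rate of 2-5% per week, equal in all phenotypes, a 10 v 15 week difference gives a spurious odds ratio of about 1.6-1.7, and equal timing gives 1.00. A reader might take the odds ratios of about 6 to 8 at the limits of the windows as the likely bias. They are not: they need a complete separation of OGTT timing that nothing in the protocol suggests.

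The number of women who would have no visit 2 cannot be estimated from the protocol. This is an inexpensive improvement, not a defect that invalidates the aim.

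**What to change.** - In section 6.3, add the date of first metformin or insulin, abstracted from the medical records already being accessed, for every woman with GDM.
- In section 11.2 b, add time from OGTT to first medication, censored at delivery, as an Aim 2 analysis. Women who deliver before 34-36 weeks then contribute.
- Keep the ordinal logistic regression. Define its outcome as the highest treatment level from diagnosis to delivery, taken from the delivery record, and include gestational age at OGTT in the model. The second and third categories overlap as worded and need separating for a highest level to be well defined.
- If start dates will not be collected, remove *immediate* from the Aim 2 hypothesis so that it matches the late-pregnancy outcome.

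The cost is one extra date field for about 200 women, one extra analysis and a change of protocol wording. No visit, procedure or aspect of care changes. Replacing the ordinal outcome altogether is not required; it carries the treatment level that the protocol sets out to study.

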Hypothesis: With comprehensive information on continuous glycemic profiling (i.e. greater glycemic variability), clinically established biomarkers (i.e. greater HOMA-IR) and targeted metabolites (i.e. greater Acylcarnitines) in early pregnancy, a prediction model for GDM might be applicable.

2.1. Potential Risks and benefits:

a. End Points - Efficacy

Diabetes begets diabetes. This vicious cycle needs to be interrupted if diabetes epidemic is to be combatted. We are addressing one of Singapore's major health challenges – the very high prevalence of GDM during pregnancy, and its future development of abnormal glucose metabolism in mothers, and accumulated adiposity in their offspring. Categorization of GDM phenotypes may have further implications on patient-related outcomes, such as guiding targeted pregnancy care, offspring outcomes (i.e. macrosomia), and maternal outcomes (i.e. postnatal glucose intolerance). The patient-related outcomes are trans-generational and studying the pathophysiological link between mother and child is critical for developing more efficient and precise screening approaches or targeted interventions to disrupt the vicious cycle.

b. End Points - Safety

All clinical visits are under the routine care of O&G specialists. The nature of the study is observational and we do not foresee any safety issue at the end of the study.

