3.2. Criteria for Recruitment

This is a prospective longitudinal study based on NUH O&G outpatient clinic. A cohort of 800 pregnant women will be recruited at NUH over a period of 18 months.

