11. SAMPLE SIZE AND STATISTICAL METHODS

11.1. Determination of Sample Size

Based on our prior unpublished Asia-Pacific collaborative study on both Chinese and Indians overweight and obese pregnant subjects ($BMI \geq 23 \text{ kg/m}^2$), the effect size based on analysis of variance (ANOVA) for comparison of glucose across five groups will be more than 0.60 (large effect size). Considering a local setting in Singapore that might carry lower effect size in glycemic difference between GDM phenotypes, we are considering a moderate effect size (0.3) for the sample size calculation. As we will be interested in comparing 10 outcomes, the sample size of 200 participants with GDM and overweight/obese will be sufficient to detect a difference of 0.3 effect size across five GDM phenotype with 80% power and 0.5% type-I error (applying Bonferroni correction for 10 multiple comparisons to control type-I error rate to 5%) and 10% drop-out rate. The sample size assumes prevalence of GDM phenotypes at 20% for fasting glucose impairment alone ($n = 40$), 60% for post-challenge glucose abnormality alone ($n = 120$), and 20% for both fasting and post-challenge glucose abnormality ($n = 40$).

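### Stepwise logistic regression, one of two selection methods named for the exploratory GDM prediction model, would give an unreliable variable list and too-extreme risks if the candidates are many

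*Protocol*

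**What the plan says.** Protocol section 2 sets Exploratory Aim 1: "To use machine learning to develop a prediction model for GDM diagnosis in the first trimester". The hypothesis under that aim names continuous glucose profiling together with "clinically established biomarkers (i.e. greater HOMA-IR) and targeted metabolites (i.e. greater Acylcarnitines) in early pregnancy" as the inputs. It does not say how many candidates there will be.

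Section 11.2(c) gives the method: "both stepwise logistic regression and ensemble random forest methods will be applied for variable selection". The paragraph ends with a bracketed drafting note saying that it still has to be filled out. It states no entry or removal threshold, no performance measure and no validation scheme.

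Sections 3.2 and 1.2 give the size: "A cohort of 800 pregnant women will be recruited at NUH over a period of 18 months", of whom about 200 are expected to have GDM. The sample-size paragraph (11.1) allows for 10% drop-out. That paragraph concerns the phenotype comparison; the prediction model has no sample size of its own.

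**The concern.** Stepwise logistic regression is a method the protocol chooses, not a detail it leaves open, so an analysis plan that follows the protocol inherits it. When candidates are numerous relative to events, significance-driven selection admits variables by chance and keeps the coefficients that happen to be large in the sample. Three things follow: a variable list that would change in another sample, predicted risks that are too spread out, and discrimination that looks better in the selection data than it is.

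Section 1.1 looks ahead to using early-pregnancy metabolite and biomarker signatures for more timely prevention. A list containing chance findings, or exaggerated risks, would be a poor starting point for that work.

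**Working it through.** The protocol gives no figure for this model, so there is nothing to reproduce. The check is by simulation.

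**Inputs from the protocol.** 800 women and about 200 GDM cases (sections 3.2 and 1.2); 10% drop-out (section 11.1). If drop-out applies to everyone, 800 × 0.9 = 720 women and 200 × 0.9 = 180 cases.

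**Assumptions.** The number of candidates p runs from 10 to 200. Entry is at p<0.05. Candidates are independent and normally distributed unless stated. Each setting has 20 to 40 replicates, so the second decimal of an AUC is approximate.

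**Events per candidate.** 200/p = 20, 10, 4, 2 and 1 for p = 10, 20, 50, 100 and 200.

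**Pure noise (true AUC 0.50).** A 5% entry test should admit about 0.05 × p noise variables: 2.5, 5 and 10 at p = 50, 100 and 200. Stepwise entry with removal at p>0.10 gave:

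| p | Variables kept (800 / 720 women) | Apparent AUC, 800 women | Apparent AUC, 720 women | 5-fold CV, selection done once on all data (800 women) | 5-fold CV, selection repeated in each fold (800 women) |
|---|---|---|---|---|---|
| 10 | 0.35 / 0.5 | 0.51 | 0.52 | 0.51 | 0.50 |
| 20 | 0.8 / 0.7 | 0.54 | 0.53 | 0.53 | 0.50 |
| 50 | 2.4 / 2.9 | 0.58 | 0.59 | 0.57 | 0.50 |
| 100 | 5.4 / 5.3 | 0.62 | 0.63 | 0.60 | 0.49 |
| 200 | 11.5 / 11.5 | 0.68 | 0.69 | 0.65 | 0.50 |

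Optimism is apparent AUC minus 0.50. It runs from 0.58 − 0.50 = 0.08 to 0.69 − 0.50 = 0.19 for 50 to 200 candidates, and from 0.01 to 0.04 for 10 to 20. Cross-validating only after selecting on all the data removes little of it. Repeating the selection in each fold removes it.

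**Correlated noise.** With correlation 0.5 within blocks of ten (720 women), apparent AUC at p = 50, 100 and 200 was 0.56, 0.61 and 0.67. The bias shrinks but remains.

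**Five real predictors (true AUC about 0.69, 800 women).** Apparent versus new-data AUC was:
- p = 20: 0.70 vs 0.68, difference 0.02
- p = 50: 0.71 vs 0.66, difference 0.05 from these rounded values
- p = 100: 0.73 vs 0.65, difference 0.08

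With 720 women and p up to 200 the difference reaches about 0.14. Across settings with 10 to 20 candidates it stays within about 0.01 to 0.06.

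**Variable list and calibration, five real predictors, 720 women.** At p = 100 stepwise kept 9.6 variables on average, 5.0 of them noise; at p = 200 it kept 15.6, of which 10.9 were noise. The calibration slope is b in logit P(GDM) = a + b × (model's linear predictor), fitted in new women; b below 1 means the predictions are too extreme. Two sets of runs gave 0.70–0.78, 0.53–0.61 and 0.37–0.42 at p = 50, 100 and 200. At a slope of 0.53, a predicted odds ratio of exp(1) = 2.72 between two women corresponds to exp(0.53) = 1.70 in reality.

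**Comparison with LASSO.** On pure noise, cross-validated LASSO typically kept no variable. With real predictors, new-data AUC for stepwise versus LASSO was 0.669 vs 0.668, 0.646 vs 0.654 and 0.630 vs 0.652 at p = 50, 100 and 200. The differences are −0.001, 0.008 and 0.022. LASSO over-shrank (slope 1.3 to 1.6), and its apparent AUC was optimistic too.

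**The case against.** A reader might infer that the study will report discrimination that does not exist. The protocol does not support that. Section 11.2(c) names no performance measure and does not say that the model will be assessed in the women used for selection. Validation may be set out in an analysis plan that is not shown, so its absence is no fault here. The table bears this out: with selection repeated in each fold, stepwise itself returns an AUC of about 0.50 on noise. Where real predictors exist, AUC is inflated rather than invented.

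A reader might also take stepwise to be the only method. It is one of two, and random forest is named beside it. Nor does the protocol say that the metabolites are numerous: the panel is described as targeted, with no count, and at 10 to 20 candidates the problem is minor. Finally, the aim is exploratory, the paragraph is marked as unfinished, and the women receive routine care (section 8.1), so nothing in this study acts on the model.

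All of this stands and limits the point. It does not remove it. Sound validation would give an honest AUC, but the final stepwise model would still carry the noise variables and exaggerated risks shown above, and the random forest does not repair that model.

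**Conclusion.** The point holds in a conditional form. With about 180 to 200 GDM cases and 50 to 200 candidates, stepwise selection at p<0.05 gives an unreliable variable list and a calibration slope of about 0.7 down to 0.4 in new women. The AUC optimism of 0.08 to 0.19 (noise) or 0.05 to 0.14 (real predictors) arises only if the selection is not repeated within validation. The sizes rest on assumed candidate counts, an assumed entry threshold and mostly independent predictors.

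The case for replacing stepwise is the variable list and calibration. It is not a better true AUC, where the gain was nil to about 0.02. Priority is low: the primary and secondary analyses do not depend on this model.

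**What to change.** In section 11.2(c), replace stepwise logistic regression with penalised logistic regression (LASSO or elastic net), keeping the random forest beside it. For both methods, repeat all variable selection and tuning inside nested cross-validation or within each bootstrap sample. Report optimism-corrected AUC and calibration. State the number of candidate predictors once the panel is fixed.

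The cost is a few sentences, in a paragraph that is already due for completion, and some computing time. No extra participants, visits or samples are needed. The reported AUC will be lower than an uncorrected stepwise one, and penalisation may over-shrink somewhat, which the calibration report would show.
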